5.3.1.3 Change and Percentage Change from Baseline

Change from baseline will be calculated as:

$$\text{change from baseline} = \text{value at timepoint} - \text{baseline value}$$

Change from baseline will be presented to the same level of precision as the original value in the listings.

Percentage change from baseline will be calculated as:

$$\text{percentage change from baseline} = 100 * (\text{change from baseline} / \text{baseline value})$$

Percentage change from baseline will be presented to 1 decimal place (dp) in the listings.

5.3.2 Demographic and Background Data

5.3.2.1 Age

Age (years) will not be recalculated using year of birth but will be taken directly from the CRF.

If participants aged >65 years are allowed to be entered into the study, then age (years) will be categorized as follows:

- 18-65 years
- 66-75 years
- >75 years

In addition, for age as a prognostic marker for COVID-19, a further categorization will be performed as follows:

- 18-59 years
- ≥ 60 years

5.3.2.2 Race and Ethnicity

Participants who select multiple races on the CRF will be coded as 'Mixed race'.

Race and ethnicity will also be combined in the 'Non-white or Hispanic/Latino' covariate as follows:

- 'Non-Hispanic/Latino white' – participants who select only race='White' and no other race and who select ethnicity ='Not Hispanic/Latino'
- 'Non-white or Hispanic/Latino' – all other participants

5.3.2.3 Height, Weight and Body Mass Index

Height may be recorded in cm or inches. Height in inches will be converted to height in cm as follows:

Height (cm) = Height (inches)*0.3937

Height (cm) will be presented to 1 dp in the listings.

Weight may be recorded in kg or pounds. Weight in pounds will be converted to weight in kg as follows:

Weight (kg) = Weight (pounds) * 0.4536

Weight (kg) will be presented to 1 dp in the listings.

Body mass index (BMI) will be calculated as:

BMI (kg/m²) = Weight (kg) / [height (cm)/100]²

BMI (kg/m²) will be presented to 1 dp in the listings.

BMI will also be categorized as:

- <30 kg/m²
- ≥30 kg/m²

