from this study, after discussion with the chief investigator. Inclusion in concurrent interventional studies will not be permitted. Inclusion in observational studies in parallel to this study is allowed.

Number of Participants:

Sixty subjects will be enrolled into the study and randomized in a 1:1 ratio. A further 40 subjects may be enrolled on the request of the DMC if it was felt likely to provide further beneficial information to take forward into planning future studies.

Participant Trial Duration:

This study will consist of a 14-day treatment period followed by a 28-day post-treatment follow-up visit, as described below:

[figure not shown]
- Up to 2 days for Screening and Baseline assessment period. *Note: Due to the urgent nature of the study, screening, baseline and Day 1 assessments can occur on the same day. Eligible patients will be randomized and dosed as soon as possible after eligibility is confirmed.*
- A 14-day treatment period (treatment will be stopped if the participant is admitted to ICU).
- A 28-day post-treatment period, with final follow-up via telephone assessment at Day 42.

Number of Centers:

The study will be run at multiple centers in the United States.

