7.2 Covariates and Subgroups

The following covariates will be considered as possible prognostic factors for inclusion in the analysis models described in [Section 7.2](#):

- Age ≥ 60 years (yes, no)
- Gender (male, female)
- Race (Non-Hispanic/Latino white, non-white or Hispanic/Latino)
- Baseline WHO OSCI score (4, 5)
- Time since onset of symptom at Baseline (days)
- Presence of obesity: BMI $\geq 30 \text{ kg/m}^2$ (yes, no)
- Current type 1 diabetes (yes, no)
- Current type 2 diabetes (yes, no)
- Current hypertension (yes, no)
- Other current chronic cardiovascular disease (yes, no)
- Current chronic respiratory disease (yes, no)
- Active cancer, excluding skin basal cell carcinoma or localized squamous cell carcinoma (yes, no)
- Smoking status (current smoker, not current smoker)
- Neutrophils $> 8.0 \times 10^3/\mu\text{L}$
- C-Reactive protein (CRP) $> 40 \text{ mg/dL}$

Other covariates may also be considered if emerging research into COVID-19 suggests other possible prognostic factors for outcome that can be determined from the data captured on the CRF.

Prior to database lock, the inferential primary analysis model described in [Section 9.2.2](#) will be examined on the blinded data in order to determine which baseline factors may have a prognostic effect on the efficacy endpoints. Covariates will be selected for inclusion in the model using forward stepwise selection procedure with a 5% level of significance applied for both the selection and deselection of variables from the model.

Where applicable, the baseline value of the endpoint will be automatically fitted first, regardless of significance before additional covariates are considered. A maximum of 3 covariates, in addition to the

baseline value where applicable, may be selected for each model in order to avoid over-parameterization and a reduction in the efficiency of treatment estimates.

If, during the study, a new treatment is approved for use in COVID-19 and becomes part of the standard of care for hospitalized participants at the study site(s), additional sensitivity analyses will be performed using covariates defined by use of this treatment.

- For ANCOVA analyses of trough S/F ratio
 - New SOC covariate: 'yes' if taken at any time before Day 14, 'no' otherwise
- For ANOVA analyses of S/F ratio at Day X
 - New SOC covariate: 'yes' if taken prior to Day X, 'no' otherwise
- For time-to-event analyses

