8.4 Concurrent Illnesses and Medical Conditions

All summaries of concurrent illnesses and medical conditions will be presented by treatment group and overall using the ITT population.

Concurrent illnesses and medical conditions will be classified as 'current' if the end date is on or after the date of first dose of study drug, or the condition has been marked as ongoing. Otherwise they will be classified as 'past'.

Targeted questions will be used to report the following known comorbidities for COVID-19 as part of the medical history CRF page:

- Type 1 diabetes
- Type 2 diabetes
- Hypertension
- Other chronic cardiovascular disease
- Chronic respiratory disease
- Ongoing diagnosis of cancer

In addition, other medical history and concurrent illnesses will be captured and coded using the v23.0 of the Medical Dictionary for Regulatory Activities (MedDRA®).

The number and percentage of participants reporting each relevant medical condition will be summarized together with the following potential risk factors for severe illness with COVID-19 which will be assessed from the demographic and baseline data:

- Age ≥ 60 years
- Male
- Non-white or Hispanic/Latino
- Obesity (BMI ≥ 30 kg/m²)
- Current smoker
- Baseline WHO OSCI score of 5
- Baseline neutrophils $> 8.0 \times 10^3/\mu\text{L}$
- Baseline CRP $> 40 \text{ mg/dL}$

In addition, the number and percentage of participants reporting 0, 1, 2, 3, 4, ≥ 5 potential risk factors will be summarized.

All medical history will be summarized, individually for past and current conditions. All medical history will be listed.

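### The SAP converts inches to centimetres with the inverse factor (0.3937 instead of 2.54), so every height recorded in inches gives a BMI about 42 times too high and an obese classification

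*SAP*

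**What the plan says.** SAP 5.3.2.3 (Height, Weight and Body Mass Index) provides for two recording units: "Height may be recorded in cm or inches. Height in inches will be converted to height in cm as follows". The formula that follows is "Height (cm) = Height (inches)*0.3937". The section then gives the weight conversion, "Weight (kg) = Weight (pounds) * 0.4536", and the BMI formula, "BMI (kg/m²) = Weight (kg) / [height (cm)/100]²". BMI is split at 30 kg/m².

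The result is used in several places:

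- **SAP 7.2** lists "Presence of obesity: BMI" of 30 kg/m² or more among 15 candidate prognostic covariates. Selection is stepwise on blinded data, with at most three covariates added to the baseline value. SAP 9.1.1.2 applies the same approach to the Cox and Fine and Gray models.
- **SAP 8.3** summarises height, weight and BMI.
- **SAP 8.4** tabulates obesity as a risk factor for severe illness and reports "the number and percentage of participants reporting 0, 1, 2, 3, 4" and five or more risk factors.
- **SAP 9.4.2** tests a treatment interaction for each covariate in section 7.2, whether or not the stepwise procedure chose it.
- **SAP 16.1.1** marks Tables 14.1.2.1 (demographics) and 14.1.3.1 (risk factors) for unblinded DMC review and for production if the study stops early.

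On location, the Protocol synopsis says "The study will be run at multiple centers in the United States". No other section of either document gives a different height conversion.

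**The concern.** One inch is 2.54 cm, so a height in centimetres must be the larger number. Multiplying by 0.3937 makes it smaller. The multiplier is the right one for the opposite conversion.

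Height enters BMI squared and in the denominator, so the error is amplified and always pushes BMI upward. Among participants measured in inches the obesity flag then carries no information about obesity. What this does to the analyses depends on the mix of units:

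- **All heights in inches:** the flag is constant. It cannot be selected as a covariate, and its interaction with treatment cannot be estimated.
- **Mixed units:** the flag partly records which unit was used. If units differ by site, a site difference could appear as an obesity effect and take one of the three covariate places, or produce a spurious interaction result.

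In either case the BMI summaries, the obesity row and the risk-factor counts are wrong, and each non-obese participant measured in inches gains one false risk factor.

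**Working it through.** **Inputs**

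- Stated conversion: inches × 0.3937 (SAP 5.3.2.3).
- BMI formula: kg / (cm/100)² (SAP 5.3.2.3).
- Cut-off: 30 kg/m² (SAP 5.3.2.3, 7.2, 8.4).
- Unit definition: 1 inch = 2.54 cm.

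**Step 1: where 0.3937 comes from.** 1/2.54 = 0.3937, the number of inches in a centimetre. Dividing by it would be correct (1/0.3937 = 2.5400), but the SAP multiplies. The neighbouring pounds-to-kilograms factor, 0.4536, is in the right direction.

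**Step 2: error in height.** 2.54 / 0.3937 = 6.4516. Height is understated 6.45-fold.

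**Step 3: error in BMI.** 6.4516² = 41.62. BMI is overstated 41.6-fold.

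**Step 4: can anyone fall below 30?** The true BMI that gives a computed value of 30 is 30 / 41.62 = 0.72 kg/m². Put as weight, a person of 70 inches (27.6 cm under the rule) would have to weigh less than 30 × 0.27559² = 2.28 kg. No adult can, so the classification is the same for every participant measured in inches.

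**Step 5: examples**

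| Height | Weight | Height as written (cm) | Correct height (cm) | BMI as written | Correct BMI |
|---|---|---|---|---|---|
| 60 in | 100 lb (45.4 kg) | 23.6 | 152.4 | 812.9 | 19.5 |
| 66 in | 180 lb (81.6 kg) | 26.0 | 167.6 | 1209.3 | 29.1 |
| 68 in | 80 kg | 26.8 | 172.7 | 1116 | 26.8 |
| 70 in | 180 lb (81.6 kg) | 27.6 | 177.8 | 1075.0 | 25.8 |
| 76 in | 140 lb (63.5 kg) | 29.9 | 193.0 | 709.3 | 17.0 |

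None of these five people is obese; the rule classes all five as obese. Over heights of 60 to 72 inches and weights of 50 to 110 kg, the computed BMI runs from 622 to 1971.

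**Step 6: effect on the obesity rate.** Let p be the share of participants with height in inches and q the true obesity rate. If unit and obesity are unrelated, the reported rate is q + p(1 − q), and the mean number of risk factors per participant rises by p(1 − q). The documents do not give p. At p = 0 nothing changes; at p = 1 the reported rate is 100%.

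**Step 7: what is not touched.** The S/F ratio is SpO₂ divided by FiO₂ (SAP 5.3.3.3) and uses neither height nor BMI. The confidence-interval half-widths in SAP Table 8 do not depend on height; all 18 reproduce with t(0.975, N−2) × SD × √(4/N).

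**The case against.** The case on the other side accepts the arithmetic and concerns the consequences.

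- **It would be noticed.** Converted height and BMI appear in listings and in a demographic table that goes to the DMC. Adults 27 cm tall with a BMI above 600 are hard to overlook. This lowers the chance that the error reaches the final report, but it does not make the rule correct. SAP section 13 says the analysis datasets will not be fully validated and will be built directly from source CRF data, so later detection should not be relied on. A silent correction in the code would also be an undocumented departure from the SAP, in a variable used for covariate selection.
- **The treatment comparison is not at risk.** This largely stands. The base ANCOVA contains treatment and baseline S/F ratio; obesity enters only if selected. BMI is a pre-treatment variable, and each site receives complete 1:1 randomization blocks (SAP 5.2). A misclassified baseline covariate would mainly cost precision.
- **The mechanism is partly assumed.** This also stands. The share of heights in inches is unknown, and nothing shows that units differ by site. The loss of a constant flag and the selection of an artefact are alternatives; both cannot happen together.
- **The stakes are low.** This is a pilot without a power calculation, all analyses are labelled descriptive, and the interaction work is exploratory. That limits the damage. It does not help the baseline and risk-factor tables, which are themselves descriptive outputs and are wrong whenever the formula is applied.

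**Conclusion.** The concern holds. The conversion in SAP 5.3.2.3 is inverted, and nothing elsewhere in the documents corrects it. If it is programmed as written, BMI is 41.6 times too high for every participant with height in inches and a recorded weight, and all of them fall in the category of 30 kg/m² or above.

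The effects that follow in any case are on the height and BMI summaries, the obesity row, the risk-factor count and the obesity term in the interaction analysis. The effect on the primary, Cox and Fine and Gray models is conditional on the blinded covariate selection. The primary endpoint and the stated precision are unaffected, and no bias in the treatment effect is expected.

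The size of the overall effect depends on the unknown share of heights in inches. With all sites in the United States, and a SAP that provides for inches, that share is unlikely to be negligible. The rule is wrong rather than ambiguous and should be corrected before the blinded covariate selection.

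**What to change.** In SAP 5.3.2.3, change the formula to: Height (cm) = Height (inches) × 2.54.

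Derive BMI, the BMI category, the risk-factor count and the blinded covariate selection from the corrected height. If any of these, or any DMC table showing BMI or risk factors, has already been produced with the old formula, regenerate it and tell the DMC. A range check on derived height in the analysis dataset would guard against the same slip in code.

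The text change is one line, needs no new data and has no statistical downside. Re-running is needed only where outputs already exist.

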5.3.2.4 Smoking Pack Years

Smoking pack years will be calculated using the type of tobacco product, amount used, frequency (daily or weekly) and duration of use.

Tobacco products other than cigarettes will be converted to cigarette equivalent using the rules in [Table 2](#).

Table 2 Conversion to Cigarette-equivalent use for Other Tobacco Products

Tobacco Product	Amount	Cigarette equivalent
Pipe	1 bowl	2.5 cigarettes
Cigarillos	1 Cigarillo	2 cigarettes
Cigars	1 Cigar	4 cigarettes
Rolling tobacco	25g (1 ounce)	50 cigarettes

If frequency is reported as a weekly amount, then the daily amount smoked will be converted from weekly amount by dividing by 7.

Pack years will be calculated after all tobacco products have been converted to provide a total daily cigarette-use equivalent as:

Pack Years = Total daily cigarette-equivalent use/20 * Years smoked

If a participant reports more than one type of tobacco product or multiple periods of use, the pack years will be calculated separately for each type/period and then added together for total pack years.

5.3.2.5 Time Since Symptom Onset

Time since symptom onset at first dose will be calculated as:

Time since symptom onset (days) = Date of first dose – Date of symptom onset + 1

5.3.2.6 Presence of Co-morbidities at Baseline

A targeted medical history will be collected at the Screening visit. Participants will be considered to have each relevant co-morbidity if it is marked as 'ongoing'.

5.3.2.7 Treatment Compliance

Participants will be expected to dose twice daily with two capsules for 6 doses and then once daily with two capsules to Day 14 for a total of 17 doses.

Unless a participant enters the study too late on Day 1 to have at least a 2-hour gap between doses, they will receive two doses on Days 1-3 and one dose on Days 4-14. Participants who do not enter the study in time to receive 2 doses with at least a 2-hour gap between doses will only receive one dose on Day 1, two doses on Days 2-4 and one dose on Days 5-14.

The expected number of capsules will be calculated as per [Table 3](#).

Table 3 Calculation of Expected Dose

Subject Status	Doses received on Day 1	Number of capsules expected
Completed treatment to Day 14	Any	34
Discontinued treatment on or after Day 4	Any	=2*(Relative Study Day+3)
Discontinued treatment on Day 3	2 doses	12
	1 dose	10
Discontinued treatment on Day 2	2 doses	8
	1 dose	6
Discontinued treatment on Day 1	2 doses	4
	1 dose	2

Number of capsules taken will be calculated as:

$$\text{Number of capsules taken} = \text{Number of capsules dispensed} - \text{Number of capsules returned}$$

Treatment compliance will be taken from the dosing log.

5.3.2.8 Daily Diary Compliance

The daily diary should be completed on every day following discharge from hospital until the participant has reported at least two consecutive days with no symptoms (Q1) and a return to their usual activities (Q3).

The last day on which a daily diary is expected is defined as the earliest of the second consecutive day on which the participant reported no symptoms and a return to their usual activities and Day 42/Study day of early withdrawal from the study.

The number of days on which a daily diary is expected will be defined as:

Number of diary days expected = Date of last expected diary day – Date of discharge

The number of diary days completed will include all days on which at least questions 1-3 of the diary were answered up to and including the date of the last expected diary day. Diary days completed after Day 42 or after the second consecutive day with no symptoms and a return to their usual activities will not be included.

Daily diary compliance will be calculated as:

Daily diary compliance (%) = $100 \times \text{Number of diary days completed} / \text{Number of diary days expected}$

Daily diary compliance will be presented to 1 dp in the listings.

5.3.3 Efficacy

5.3.3.1 SpO₂

The endpoints for maximum SpO₂ and minimum SpO₂ will be calculated from available data only.

Maximum and minimum SpO₂ will be calculated for each of the following periods:

- Days 1-7
- Days 1-14
- Days 1-28
- Days 1-42

5.3.3.2 FiO₂

FiO₂ will be derived from the device used to deliver oxygen according to the rules shown in [Table 4](#). FiO₂ will be expressed to 2 dp.

Table 4 Derivation of FiO₂ values

Oxygen Delivery Method	Data collected	Derived FiO ₂ (fraction of 1)
None (room air)	N/A	0.21
Nasal cannula	Oxygen flow rate in L/min	1
		2
		3
		4
		5
		6
		7
Venturi mask or similar device	FiO ₂ recorded directly from notes as percentage (e.g. 60%) to be converted to fraction (e.g. 0.60)	
Non-invasive ventilation	FiO ₂ recorded directly from notes as percentage (e.g. 60%) to be converted to fraction (e.g. 0.60)	

Oxygen Delivery Method	Data collected		Derived FiO2 (fraction of 1)
Non-rebreathe mask	Oxygen flow rate in L/min	15	1.00
Invasive ventilation	FiO2 recorded directly from notes as percentage (e.g. 60%) to be converted to fraction (e.g. 0.60)		
High flow nasal cannula	FiO2 recorded directly from notes as percentage (e.g. 60%) to be converted to fraction (e.g. 0.60)		

5.3.3.3 S/F Ratio

The S/F ratio will be calculated as:

$$\text{S/F ratio} = \text{SpO}_2 (\%) / \text{FiO}_2 (\text{fraction of 1}).$$

The S/F ratio will be expressed to 0 dp.

Missing S/F ratios will be imputed using the rules in [Table 5](#).

Table 5 Rules for Imputation of Missing S/F Ratios on Individual Study Days 1-14

Reason for Missingness	Data Availability	Value to be Imputed
Participant died	N/A	0
Participant was discharged	N/A	Last S/F ratio recorded prior to discharge
Participant withdrawn from the study	N/A	Not imputed, value will remain as missing.
Other reason	S/F ratio available within window of +/- 1 day	Average of non-missing S/F ratios reported on the day before and day after the study day with missing data
Other reason	No S/F ratio available within window of +/- 1 day	Not imputed, value will remain as missing.

Trough S/F ratio is defined as the lowest S/F ratio reported in Days 1-14. Participants who die on or before Day 14 will have their trough S/F ratio imputed to 0.

If more than one S/F ratio is provided for a relevant study day, the lowest S/F ratio reported for that study day will be used in all summaries and analyses.

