1.3. Schedule of Activities (SoA)

Figure 2: Schedule of Activities

Data	Screening [^] (Day -1 to Day 0)	Baseline [^] (Day -1 to Day 0)	D 1 [^]	D 2	D 3	D 4	D 5	D 6	D 7	D 8	D 9	D 10	D 11	D 12	D 13	D14 or day of discharge ^{&}	D21 ~ (Follow-up Telephone Visit)	D42 (Final Follow-Up Telephone Visit)
Informed consent	x																	
Inclusion and exclusion criteria	x																	
Demographics and anthropomorphic data (e.g. age, height, weight)	x																	
Smoking status ⁹	x																	
Medical history	x																	
Significant Covid-19 Comorbidities	x																	
Physical examination	x																	
Pregnancy test (blood/urine) ¹	x																	
Vital signs ^{#*}		x	x	x	x	x	x	x	x	x	x	x	x	x	x	x		
Concomitant Medications [#]	x	x	x	x	x	x	x	x	x	x	x	x	x	x	x	x	x	
Oxygen therapy status [#]		x	x	x	x	x	x	x	x	x	x	x	x	x	x	x	x	
SaO ₂ /FiO ₂ status ^{#2*}		x	x	x	x	x	x	x	x	x	x	x	x	x	x			
Blood tests (FBC, CRP, LFT, Creatinine, Urea and Electrolytes, Ferritin, D-		x				x ³			x ³									

Data	Screening [^] (Day -1 to Day 0)	Baseline [^] (Day -1 to Day 0)	D 1 [^]	D 2	D 3	D 4	D 5	D 6	D 7	D 8	D 9	D 10	D 11	D 12	D 13	D14 or day of discharge ^{&}	D21 ~ (Follow-up Telephone Visit)	D42 (Final Follow-Up Telephone Visit)
dimer, Troponin) ^{#*}																		
HIV test	x																	
Cytokine Panel, Paxgene sample, and Biobanking sample*		x				x ³			x ³									
Plasma PCR for EDP1815									x ³									
Day since onset of symptoms [#]		x																
8-point ordinal scale [#]		x	x	x	x	x	x	x	x	x	x	x	x	x	x	x	x	x
COVID-19 RTPCR [#]	x																	
Review of adverse events ^{#*@}	x	x	x	x	x	x	x	x	x	x	x	x	x	x	x	x	x	x
Retrieval of relevant clinical data ⁴																		x
Outpatient questionnaire ⁵			x	x	x	x	x	x	x	x	x	x	x	x	x ⁶	x ⁶	x ⁶	
Telephone call ⁵								x							x	x	x	
Discharge status [#]			x	x	x	x	x	x	x	x	x	x	x	x	x	x	x	
Mortality status [#]			x	x	x	x	x	x	x	x	x	x	x	x	x	x	x	
Faecal sample for microbiome analysis		x ⁷							x ⁷									
EDP1815 or Placebo administration ⁸			x ⁸	x ⁸	x ⁸	x	x	x	x	x	x	x	x	x	x			

[^] Due to the urgent nature of the study, screening, baseline and Day 1 assessments can occur on the same day. Eligible patients will be randomized and dosed as soon as possible after eligibility is confirmed.

[~] This assessment can be performed between days 20-22.

#Results will be extracted from the patient record where available – no research specific test may be required.

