*If a patient is discharged then these assessments may not be performed.

@Whilst an inpatient, participants should have a daily assessment for evidence of nausea, vomiting, diarrhoea, bloating and abdominal pain. This information will be collected for outpatients in the patient questionnaire.

& If a participant is not discharged at Day 14 and remains in hospital, Day 14 assessments will be performed until a participant is discharged from hospital or they reach the final follow-up visit (Day 42).

¹ Pregnancy test will only be performed in women of child-bearing potential (Appendix 2).

² If the patient is on 3L/min oxygen flow or less, this assessment should be performed after the patient is at rest on room air for 10 minutes, as detailed in section 8.1.1.

³ If the patient is discharged prior to these blood tests, where possible outpatient blood testing will be organised.

⁴ Extraction of relevant clinical data from the patient's medical record (such as but not limited to symptoms, concomitant medications, other relevant blood tests, and radiology reports such as chest radiograph or CT scan).

⁵ If the patient is discharged, they will be given a daily questionnaire to complete; a telephone call will be made on day 7, 14, 21 and 42 (telephone call has a window of +/- 1 day).

⁶ The patient will be asked to continue to fill the questionnaire daily until their symptoms have fully resolved for 48 hours or until the day 42 telephone visit (whichever is earlier).

⁷ This is an optional sample for research purposes but will be collected whenever possible once at the Baseline visit and then again once between Days 5-14. If the patient is discharged prior to this faecal test, where possible, an outpatient sample will be collected.

⁸ Administered twice daily for six doses) and then once daily for the remaining days (17 doses total). Treatment will be stopped if the participant is admitted to ICU, meets individual stopping criteria, or is withdrawn from the study.

⁹ Smoking status to include whether current-smoker, ex-smoker, or never-smoker; and to quantify current usage and total pack-year history.

2. Introduction

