8.1.1. Oxygen Saturation

Oxygen saturation will be measured using a peripheral pulse oximeter and will also be analysed as a ratio with the oxygen flow ($\text{SpO}_2 / \text{FiO}_2$). The measurement will ideally be performed with the subject sitting and having been rested for at least 10 minutes.

If the subject is on 3litres/min oxygen flow or less, and the investigator feels it is safe to do so, the investigator will remove the subject's supplemental oxygen for 10 minutes while they remain seated, and while continuously monitoring the oxygen saturation. After 10 minutes the oxygen saturation reading will be taken to calculate the S/F ratio on room air. If, during this process, the saturations drop by greater than 4%, the oxygen will be immediately replaced and the ratio measured on oxygen.

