9.4.1.2. Secondary Efficacy Analyses

Change from baseline in S/F ratio at Days 4, 7, 10 and 14 will be analysed separately ANCOVA models. The models will include treatment, baseline S/F ratio together with the additional baseline covariates included in the primary model for trough S/F ratio. Two models will be fitted, one with S/F ratio as the response variable and one with change from baseline in S/F ratio as the response variable.

If more than one S/F ratio measurement is provided at the relevant study day, the lowest S/F measurement within each study day will be used. Participants who are discharged from hospital will have their last observed S/F ratio prior to discharge carried forward to replace missing data at later timepoints. Data missing for reasons other than discharge will be imputed with the closest S/F ratio recorded within one day of the missing visit if such a value exists, otherwise the participant will be excluded from the analysis for that visit.

Other mechanisms for dealing with this missing not at random (MNAR) data may be further investigated for informing on the most credible methods to take forward into a future study. These methods will be further discussed in the SAP.

LS mean and LS mean change from baseline in S/F ratio will be reported with their corresponding standard error and 95% confidence interval. Estimated treatment difference for the mean change from baseline and corresponding 95% confidence interval will also be reported.

If during the course of the study, a newly approved medication for COVID-19 becomes part of the standard of care treatment at the investigational site, a further sensitivity analysis will be performed. A new-medication covariate (yes, no for use prior to the relevant study day) and an interaction for treatment*new medication will be included in the ANCOVA models described above at timepoint.

Percentage change from baseline in S/F ratio will be analysed in the same manner as the change from baseline in S/F ratio described above.

A Cochran-Mantel Haenszel (CMH) test for ordinal data will be used to compare the treatment groups with respect the percentage of participants reporting each WHO OSCI score at Days 4, 7, 10, 14, 21 and 42.

Shift tables showing the shifts from Baseline to each of Days 4, 7, 10, 14, 21 and 42 in WHO OSCI score will be provided.

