5.3.1.2 Baseline

The last non-missing value collected before first study dose will be taken as the baseline measurement for all parameters. If data is collected on Day 1 without an associated time being provided, it will be assumed to be pre-dose.

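### Baseline and trough S/F can be read under different oxygen conditions, so a stable low-flow participant can show a false fall in the primary change

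*SAP*

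**What the plan says.** - **How S/F is measured.** Protocol 8.1.1 sets the condition: "If the subject is on 3litres/min oxygen flow or less, and the investigator feels it is safe to do so", oxygen is removed for 10 minutes under monitoring. Then "After 10 minutes the oxygen saturation reading will be taken to calculate the S/F ratio on room air". If saturation falls by more than 4%, oxygen is replaced and the ratio is measured on oxygen. Footnote 2 of the Schedule of Activities is attached to the whole S/F row, baseline included: "If the patient is on 3L/min oxygen flow or less, this assessment should be performed after the patient is at rest on room air".
- **Where the values come from.** The Schedule marks S/F as a result that may be taken from the patient record, noting that "no research specific test may be required". Protocol sections 8 and 8.1 qualify this: routine results may be used if they meet the protocol's criteria and timing.
- **Which value is analysed after baseline.** SAP 5.3.3.3: "Trough S/F ratio is defined as the lowest S/F ratio reported in Days 1-14". For days with more than one value, "the lowest S/F ratio reported for that study day will be used in all summaries and analyses". Protocol 9.4.1.2 has the same daily rule for the Day 4, 7, 10 and 14 analyses: "the lowest S/F measurement within each study day will be used".
- **Which value is baseline.** SAP 5.3.1.2: "The last non-missing value collected before first study dose will be taken as the baseline measurement for all parameters".

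No passage says which reading defines S/F when room-air and on-oxygen values exist for the same day. None requires baseline and trough to be read under the same condition.

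**The concern.** S/F divides saturation by FiO2, so the same lungs give a much higher ratio on room air (FiO2 0.21) than on a cannula, unless saturation falls steeply when oxygen is removed. Protocol 8.1.1 keeps a room-air reading only when saturation does not fall steeply. A minimum taken across both conditions will therefore favour the on-oxygen value, while a last-value baseline may be either.

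Every participant is on oxygen at entry (inclusion criterion 3), so mixed readings are foreseeable. A participant whose condition has not changed could then show a large drop in the primary endpoint, depending on which readings the site transcribed and whether the room-air test was run.

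The study has no power calculation. Its stated purposes include judging endpoint sensitivity and informing the sample size of later studies, so the SD of this change is one of its main products. SAP 7.4.3 also ties the recommendation to extend to 100 participants partly to the size of the variation.

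**Working it through.** **Inputs.** Room-air FiO2 is 0.21 (SAP Table 4), and S/F = SpO2 (%) / FiO2 (SAP 5.3.3.3). A completed room-air test allows a fall of at most 4 (protocol 8.1.1), read here as percentage points. The derived FiO2 values for nasal cannula cannot be read in the available text of Table 4. I assume 0.24, 0.28 and 0.32 at 1, 2 and 3 L/min; their absence is not a fault of the plan.

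**1. The plan's own figure.** Half-width = t(0.975, N−2) × SD × √(2/(N/2)). For N = 60 and SD 100: 2.0017 × 100 × √(2/30) = 51.7, as in SAP Table 8. All 18 entries of that table reproduce to one decimal.

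**2. When the minimum rejects the room-air reading.** With on-oxygen saturation S and a fall of 4, on-oxygen S/F is lower when FiO2 > 0.21 × S/(S−4).
- S = 92: 0.21 × 92/88 = 0.2195
- S = 96: 0.21 × 96/92 = 0.2191
- S = 85: 0.21 × 85/81 = 0.2204, the largest value for S from 85 to 100

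Smaller falls lower the threshold. Above an FiO2 of about 0.22, the on-oxygen value is therefore the smaller of the two for a stable participant.

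**3. Size for one stable participant** at 96% on oxygen and 92% on room air. Room-air S/F = 92/0.21 = 438.

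| Assumed FiO2 | On-oxygen S/F | False change |
|---|---|---|
| 0.24 | 96/0.24 = 400 | −38 |
| 0.28 | 96/0.28 = 343 | −95 |
| 0.32 | 96/0.32 = 300 | −138 |

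Across SpO2 90-98%, falls of 0-4 points and FiO2 0.24-0.32, the range is −35 (375 − 410) to −160 (306 − 467).

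**4. Which sentence does what.** The minimum of daily minima equals the minimum of all readings. For the primary endpoint the trough sentence alone produces the effect, and deleting the lowest-of-day sentence would change nothing. The daily sentence matters for Days 4, 7, 10 and 14.

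**5. Effect on the SD.** If a fraction p carries an artefact d, SD becomes √(SD² + p(1−p)d²). With d = 95 and N = 60:

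| Starting SD (half-width) | p = 0.25 | p = 0.50 |
|---|---|---|
| 100 (51.7) | 108.1 (55.9) | 110.7 (57.2) |
| 50 (25.8) | 64.7 (33.5) | 69.0 (35.6) |

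The values of p are assumptions, and the calculation is before adjustment for baseline S/F.

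**6. Effect on the comparison between arms.** I simulated 60 stable participants with no treatment effect: FiO2 0.28, room-air falls uniform on 0-4, 14 days, 1,000 replicates. The mean change was −110 with a room-air baseline and all later readings, −8 with room-air readings throughout, and −6 with an on-oxygen baseline and all later readings. The mean difference between arms was about 0 in all three.

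**The case against.** Several points against this carry weight.

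- **Baseline need not be on room air.** A reader might infer that baseline always keeps the room-air value, so that the primary change generally shows a decline that did not happen. The documents do not support that. The last pre-dose value may be on oxygen because flow exceeded 3 L/min, the test was judged unsafe, saturation fell too far, or a routine reading came later. The false fall is conditional.
- **Routine readings may not qualify.** Protocol sections 8 and 8.1 can be read to exclude an ordinary on-cannula reading when the room-air test was completed. This is a fair reading. However, SAP 5.3.3.3 still provides for several S/F values in a day and does not apply that filter. Whether the CRF collects several values cannot be seen.
- **It is not an SAP departure.** The daily rule is also in protocol 9.4.1.2, and the protocol's primary endpoint is itself the lowest S/F in Days 1-14.
- **It does not bias the treatment comparison by itself.** A reader might infer that it does. Under blinded 1:1 allocation the artefact falls on both arms alike. It could become differential only if treatment changed how often on-oxygen readings are taken, which the documents do not establish. ANCOVA on baseline S/F also absorbs part of it, although the model has no term for measurement condition.
- **A same-day rule leaves a remainder.** Trough is a 14-day minimum, so one day without a completed room-air test brings the mixed condition back. If the test is completed independently with probability 0.9 per day, the chance of at least one such day is 1 − 0.9^14 = 77% (51% at 0.95). This stands, and is why the fix needs a like-for-like sensitivity analysis.
- **The study is a descriptive pilot.** SAP Table 8 allows SDs of 50 to 150, and the inflated values above lie inside that range. This limits the severity.

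**Conclusion.** The concern holds in a conditional form. When room-air and on-oxygen readings are both reported, the minimum selects the on-oxygen value at any derived FiO2 above about 0.22. A stable participant whose baseline was on room air can then show a false fall of about 35 to 160 points. The direction follows from the S/F formula and the 4-point limit. The size rests on assumed cannula FiO2 of 0.24-0.32, and the effect on the SD also rests on an assumed 25-50% of participants affected.

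The consequence is added noise in the primary change and in the Day 4, 7, 10 and 14 values, and an inflated SD carried into future planning. At SD 100 the half-width rises from 51.7 to about 56-57; at SD 50, from 25.8 to about 34-36. Calling the endpoint uninterpretable would go too far. This is a should-fix, not a must-fix.

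**What to change.** Write one reading rule and apply it in SAP 5.3.1.2, in both the trough sentence and the lowest-of-day sentence of SAP 5.3.3.3, and in protocol 9.4.1.2:

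1. Only readings that meet the 8.1.1 criteria qualify as S/F data, consistent with protocol section 8.
2. Where a completed 8.1.1 room-air reading exists for a day, it is used in place of on-oxygen readings at 3 L/min or less that day.
3. Readings above 3 L/min or on other devices always count. On-oxygen readings count on days without a completed room-air test.
4. Take the lowest of what remains. For baseline, apply the same rule to pre-dose readings only.

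Flag the measurement condition in the S/F listing. Add a sensitivity analysis of change to trough that uses only post-baseline readings taken under the same condition as baseline (room air or oxygen).

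**Cost.** SAP wording, a matching protocol edit, and programming before database lock. Delivery method is already collected to derive FiO2.

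**Downsides.** Some low-flow daily values become higher. A genuine same-day fall on low-flow oxygen after a completed test would not count that day. Days without a completed test remain mixed in the main analysis. The sensitivity analysis may lose days, including on-oxygen days of a room-air-baseline participant who truly worsens, so it supports the main analysis and does not replace it.
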